**1.0 Background**

Tacrolimus is the standard immunosuppressive drug used to prevent organ rejection post liver transplant. One side effect of Tacrolimus is nephrotoxicity. Everolimus does not have the nephrotoxicity side effects of Tacrolimus. Replacement of Tacrolimus by Everolimus may have a reduced incidence of renal dysfunction in liver transplant patients who already have chronic kidney disease or peri-operative acute kidney injury. Our liver transplant patients receive potent induction immunosuppression in the form of rabbit anti thymocyte globulin. We believe that in conjunction with this induction regimen, patients can be maintained on Everolimus monotherapy without the risk of rejection. Additionally, Everolimus is known to induce tolerance in transplant recipients. Tolerant patients do not require immunosuppression to accept transplant organs.

**2.0 Rationale and Specific Aims**

Tacrolimus is a widely used in liver transplant recipients for immunosuppression, however it is associated with nephrotoxicity. Everolimus, on the other hand lacks nephrotoxicity. Whether replacement of tacrolimus by Everolimus preserves kidney function in patients with pre-existing chronic kidney disease or acute kidney injury is not well established. Also, the efficacy and safety of reduced-dose Everolimus with or without mycophenolic acid (Cellcept or Myfortic) in prevention of rejection is unknown.

**Primary Aim**

Assess the effect of Everolimus with or without mycophenolic acid versus Tacrolimus plus mycophenolic acid therapy on renal function measured by Glomerular Filtration Rate (GFR).

**Secondary Aims**

Compare the efficacy of Everolimus plus mycophenolic acid versus Tacrolimus plus mycophenolic acid therapy as measured by the following:

- Biopsy-confirmed acute rejection
- Hyperlipidemia
- Proteinuria

- NODAT [New Onset Diabetes mellitus After Transplant], hypertension and malignancy

### **3.0 Study Plan, Experimental Design, and Methodology**

The proposed investigation will be a single-center, randomized, open-label, active control comparison of the standard renal dysfunction maintenance immunosuppression regimen of reduced-dose Tacrolimus plus mycophenolic acid (control arm) versus Everolimus in combination with mycophenolic acid (study arm).

### **4.0 Inclusion/Exclusion Criteria**

List Inclusion criteria:

- Liver transplant recipients  $\geq$  18 years old
- Renal dysfunction (GFR  $\leq$  60 mL/min) at 30 days post-operatively +/- 7 days
- Rabbit anti-thymocyte globulin (rATG) induction (at least 1 dose)
- Indication for transplant: ethanol, hepatitis C, or nonalcoholic steatohepatitis

List Exclusion criteria:

- Increased risk of rejection: autoimmune hepatitis, primary biliary cirrhosis, primary sclerosing cholangitis, positive crossmatch, retransplantation
- Incompletely healed incision or other wound healing issues at time of randomization
- Multiple or previous organ transplantation
- Severe, uncontrolled hypercholesterolemia ( $> 9$  mmol/L) or hypertriglyceridemia ( $> 8.5$  mmol/L) in the 6 mo prior to transplantation
- Insurance company unwilling to pay for the cost of the everolimus
- Pregnant women
- Unable to provide informed consent

### **5.0 Enrollment/Randomization**

Following transplant, prior to the one month post-transplant visit, all eligible subjects will be approached either in the transplant unit in the hospital or at the transplant clinic in the hospital for study participation. A random permuted block design will be used to generate random assignments to the groups. This method will ensure balance across the groups over the course of the study period. The biostatistician at the Center for Outcomes Research in Surgery will prepare the master randomization assignment list. Clinical research coordinator will then administer randomization. Since this is an open label study, care providers will not be blinded to the randomization. We do not believe this will interfere with the results of the study or patient care.

Following enrollment, subjects will be randomized at one month post transplant to reduced dose Tacrolimus plus mycophenolic acid (control group) or to Everolimus plus mycophenolic acid (study group) maintenance immunosuppression.

A previous Phase III study (Baboolal, 2003) showed that the mean creatinine clearance rate – a measure to assess the kidney function post-transplant – in the treatment group (those receiving Sirolimus and a CNI (Cyclosporine or Tacrolimus) with planned withdrawal of the CNI) was 65mL/min (SD=14) and in the control group (those who continued to receiving Sirolimus and a CNI) it was 57mL/min (SD=13). Therefore, using the two independent-groups and two-tail t-tests, we will need to recruit 46 patients in each group. With an attrition rate of 11% (Baboolal, 2003), we approximately need 104 participants in this study (52 subjects in each arm) to achieve a statistical power of 80% at 0.05 level of significance. Power analysis and sample size calculation were done using G\*Power 3.1.9.2.

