### **RANDOMIZATION:**

On POD 30, patients meeting study criteria will be randomized to either the study arm or control arm. Patients randomized to the study arm will be converted to Everolimus (target trough levels 4-8 ng/mL) plus mycophenolic acid (Cellcept or Myfortic) therapy. mycophenolic acid dose as deemed appropriate per standard of care. Everolimus will be initiated at 1mg BID. Tacrolimus will be discontinued once Everolimus level is within goal

range, or at the discretion of the provider. The control arm will be maintained on the low dose Tacrolimus plus mycophenolic acid therapy.

At 3 months, patients with GFR ≤60 will proceed to reduced dose Everolimus (target trough levels 3-6 ng/mL) plus mycophenolic acid therapy. Patients with GFR >60 will proceed to Everolimus monotherapy (target trough levels 4-8 ng/mL).

If deemed clinically appropriate, mycophenolic acid may be held for up to 2 weeks.

Complete blood counts, liver function panels, and drug levels will be monitored as done Standard of Care [SOC]: initially twice per week for first month, once per week for next two months, once every other week for next three weeks, and then once monthly. Ultrasound, ERCP, biopsy as needed by clinical situation as SOC.

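### Does the silence of Section 5.0 on allocation concealment, at one open-label site using permuted blocks, call for a change to the plan?

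*Combined protocol and SAP*

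**What the plan says.** Section 3.0 describes a "single-center, randomized, open-label, active control comparison". Section 5.0 adopts random permuted blocks without giving a block size. It then divides the work: the biostatistician "will prepare the master randomization assignment list. Clinical research coordinator will then administer randomization". It adds: "Since this is an open label study, care providers will not be blinded to the randomization".

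On the order of events, Section 5.0 states "Following enrollment, subjects will be randomized at one month post transplant", and the randomization part of Section 6.0 states "On POD 30, patients meeting study criteria will be randomized to either the study arm or control arm".

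Three criteria in Section 4.0 matter here:
- the qualifying GFR, taken "at 30 days post-operatively +/- 7 days";
- an exclusion for "Incompletely healed incision or other wound healing issues at time of randomization";
- an exclusion for "Insurance company unwilling to pay for the cost of the everolimus".

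Section 11.0 specifies an intent-to-treat analysis with a repeated-measures model. Section 12.0 mentions REDCap for data storage only. No section names a concealment method or a recorded eligibility check before an assignment is released.

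**The concern.** Blinding and concealment are different safeguards. An open-label trial can still hide the next assignment, and Section 5.0 speaks only to blinding. At a single open-label centre every past assignment is visible, which is the setting in which permuted blocks can be predicted. If the coordinator could also read the list, every assignment would be known in advance.

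The wound-healing exclusion is a clinical judgement made at the moment of randomization. Someone who knew or guessed the next arm could apply it more strictly for one arm than for the other. That selection would precede randomization, so intent-to-treat analysis would not undo it. Adjustment for baseline GFR would not remove unmeasured differences in expected renal recovery. The insurer exclusion concerns only the study-arm drug and has no stated time of check, which raises the further worry that exclusions might fall in one arm only. At stake is a spurious difference in GFR, the primary outcome.

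**Working it through.** **The plan's own figure.** Section 5.0 gives means of 65 and 57 mL/min, with SDs of 14 and 13. The difference is 8. The pooled SD is √((14² + 13²)/2) = 13.51. The exact two-sided t test at 0.05 with 80% power needs 45.74, so 46 per group. Then 46/(1 − 0.11) = 51.7, so 52 per arm and 104 in total. The plan's figure reproduces, and the concern does not touch it.

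**Predictability.** The block size is not in the documents. Assume fixed 1:1 blocks of known size, with every past assignment tracked. Enumerating all balanced blocks gives the share of assignments that are certain and the success rate *p* of guessing the arm with more places left (coin toss at ties).

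| Block size | Certain | Of 104 | *p* |
|---|---|---|---|
| 2 | 50% | 52 | 0.750 |
| 4 | 33% | 35 | 0.708 |
| 6 | 25% | 26 | 0.683 |
| 8 | 20% | 21 | 0.666 |

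**Bias.** Suppose selection moves a patient's expected GFR by *d* in favour of the guessed arm. Each arm's mean then moves by *d*(2*p* − 1), in opposite directions, so the false difference is 2*d*(2*p* − 1). A visible list means *p* = 1 and a false difference of 2*d*. For a hidden list:

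| Block size | False difference | Share of visible-list bias removed by hiding |
|---|---|---|
| 2 | 1.00*d* | 50% |
| 4 | 0.83*d* | 58% |
| 6 | 0.73*d* | 63% |
| 8 | 0.66*d* | 67% |

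**False-positive rate.** Take the planning t test with 46 per arm: SE = 13.51 × √(2/46) = 2.82, with 90 df and a noncentral t distribution. For *d* = 1, 2, 3 mL/min:
- visible list: false difference 2, 4, 6 mL/min; rate 10.8%, 29.0%, 55.9%;
- hidden list, every best guess acted on, blocks of 4 to 8: 0.7–0.8, 1.3–1.7, 2.0–2.5 mL/min; rate 5.6–6.0%, 7.5–9.0%, 10.8–14.2%;
- hidden list, blocks of 2: 1, 2, 3 mL/min; rate 6.4%, 10.8%, 18.4%.

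**Varied blocks.** Simulating block sizes drawn at random from {4, 6} and from {4, 6, 8} gives 5.6% and 2.3% of assignments certain, but best-guess bias of 0.77*d* and 0.72*d*. That is close to the fixed-block values, and fixed blocks of 8 (0.66*d*) do slightly better.

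**What the text settles.**
- *Access to the list.* Section 5.0 says who prepares the list and who administers randomization. It states no handover. Administering assignments is compatible with receiving them one at a time.
- *Order.* Section 6.0 randomizes patients who meet the criteria, so every listed criterion, including the insurer's decision, comes before assignment.
- *Late refusal by an insurer.* Intent-to-treat in Section 11.0 keeps such a patient in the assigned arm. One-sided exclusion would require departing from both Section 6.0 and Section 11.0.
- *GFR.* Table 1 schedules one GFR at day 30 ± 7, that is, days 23 to 37, and Section 7.0 adds no study visits. There is little room to choose among values.

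**The case for a change.** The strongest case for a change is that selection bias cannot be reliably repaired after enrolment and that a few sentences in Section 5.0 would be cheap. The text has no concealment method, no block size and no recorded eligibility step, and Section 5.0 reads as complete prose, so removed text does not explain the silence. The wound-healing exclusion is a real point of discretion at the moment of allocation. All of this stands as a description of what is unwritten.

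It does not show a defect in the design. No stated rule gives a wrong result, and each safeguard one might write in is already permitted by the present text. The insurer route falls away for the reasons given in the working. The larger false-positive rates need a list that staff can read, selection acting on every assignment, and a shift *d* that the documents do not supply. No passage links wound healing to later renal function. The rates also come from the planning t test, not the repeated-measures model. Nor are they upper bounds if the block size is taken to start at 4, as the figures for size 2 show. Varying the block sizes would scarcely reduce the bias from guessing, and any permuted-block scheme at an open-label site leaves some of it.

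**Conclusion.** No change to the plan follows. Section 5.0 leaves out operational detail that a biostatistician holding the list and a coordinator running allocation would ordinarily settle by releasing assignments one at a time after eligibility is confirmed. Followed that way, the plan supports a sound comparison. What remains is guessing from past assignments, a known cost of permuted blocks in an open-label trial. Under the assumptions above (fixed blocks of 2 to 8 known to staff, every best guess acted on, *d* of 1 to 3 mL/min), that is at most about 0.7 to 3 mL/min against the planned difference of 8.

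The conclusion rests on reading Section 5.0 as silent on who sees the list, not as giving it to the coordinator, and on Section 6.0 meaning what it says about criteria being met first. Evidence that staff could in fact read upcoming assignments would change the assessment. The documents contain none.

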## **6.0 Study Procedures**

After liver transplant, all patients will receive the standard induction regimen and Tacrolimus monotherapy.

### **INDUCTION:**

Rabbit anti-thymocyte globulin (rATG) 1.5 mg/kg of actual body weight rounded to nearest 25 mg and capped at 150 mg for up to three doses given IV on post-operative day (POD) 1, 3, and 5. Some patients may receive only one dose if they are considered too frail to need all three doses.

30 minutes prior to infusion, pre-medicate with the following:

Daily steroid dose

Acetaminophen (Tylenol®) 650 mg PO or per NG x 1 dose

Diphenhydramine (Benadryl®) 25 mg IV push x 1 dose

### **Steroids:**

Methylprednisolone (Solu-Medrol®) 250 mg IV push x 1 dose on POD 1 (given 30 minutes prior to rATG) and 125 mg IV push x 1 dose on POD 3.

### **Maintenance:**

Low dose Tacrolimus (FK / Prograf®) (titrated to a goal trough of  $5 \pm 1$  ng/mL) plus mycophenolic acid (Cellcept or Myfortic).

### **RANDOMIZATION:**

On POD 30, patients meeting study criteria will be randomized to either the study arm or control arm. Patients randomized to the study arm will be converted to Everolimus (target trough levels 4-8 ng/mL) plus mycophenolic acid (Cellcept or Myfortic) therapy. mycophenolic acid dose as deemed appropriate per standard of care. Everolimus will be initiated at 1mg BID. Tacrolimus will be discontinued once Everolimus level is within goal

range, or at the discretion of the provider. The control arm will be maintained on the low dose Tacrolimus plus mycophenolic acid therapy.

At 3 months, patients with GFR ≤60 will proceed to reduced dose Everolimus (target trough levels 3-6 ng/mL) plus mycophenolic acid therapy. Patients with GFR >60 will proceed to Everolimus monotherapy (target trough levels 4-8 ng/mL).

If deemed clinically appropriate, mycophenolic acid may be held for up to 2 weeks.

Complete blood counts, liver function panels, and drug levels will be monitored as done Standard of Care [SOC]: initially twice per week for first month, once per week for next two months, once every other week for next three weeks, and then once monthly. Ultrasound, ERCP, biopsy as needed by clinical situation as SOC.

## **7.0 Data to be Collected**

Target Population: Liver-only transplant patients

Baseline Information: Demographics (age, race, sex, BMI), pre-treatment medical history, pre-treatment concomitant medication.

Intervention: The treatment period starts at 30 days post transplant. Subjects will be followed for up to a total of 36 months post transplant.

During the treatment period relevant concomitant medications, adverse events, complete blood counts, liver function panels, and immunosuppression drug levels will be collected.

Follow-up: Data will be collected at 6 month, 12 month, 24 month, and 36 month timepoints. GFR will be measured at these time points. Any biopsy confirmed rejection that occurs on or before the 36 month timepoint will be recorded. See Table 1 for timeline for data collection.

Occurrence or change in NODAT [New Onset Diabetes mellitus After Transplant], neurocognitive function, hypertension, malignancy, and tolerance will be recorded throughout the length of the study. Results of any ultrasound, ECRP, or biopsy performed for clinical reasons will be recorded throughout the study.

Study follow up will be conducted per standard of care. Patients will not undergo any additional visits for study purposes during treatment or follow up.

Table 1

	days										Months					
	0	1	7	14	21	30 	2 	3 	4 	5 	6 	9 	12 	18 	24 	36 
Sr Creatinine	x	x	x	x	x	x	x	x	x	x	x	x	x	x	x	x
Creatinine Clearance	x	x	x	x	x	x	x	x	x	x	x	x	x	x	x	x
MDRD GFR	x	x	x	x	x	x	x	x	x	x	x	x	x	x	x	x
Sr Glucose	x					x	x	x	x	x	x	x	x	x	x	x
Urine Protein	x					x	x	x	x	x	x	x	x	x	x	x
Lipid profile	x					x	x	x	x	x	x	x	x	x	x	x
BP	x					x	x	x	x	x	x	x	x	x	x	x
LFT	x	x	x	x	x	x	x	x	x	x	x	x	x	x	x	x
Everolimus level							x	x	x	x	x	x	x	x	x	x
Tacrolimus level	x	x	x	x	x	x	#	#	#	#	#	#	#	#	#	#

# control patients

1. +/- 7 days

2. +/- 1 month

## 8.0 Drug Information

Please see the “CellCept\_PM\_E,” “Myfortic,” “Prograf-Tacrolimus,” and the “Zortress Package Insert” attachments.

## 9.0 Reporting of Adverse Events or Unanticipated Problems involving Risk to Participants or Others

### Definitions of Adverse Events

#### Adverse Event (AE)

An **adverse event** is defined as untoward medical occurrence associated with the use of a drug or procedure in humans, whether or not considered drug or procedure related. An adverse event can be **ANY** unfavorable and unintended sign, symptom, or disease temporarily associated with the use of a medicinal (investigational) product or procedure, whether or not considered related to the medicinal (investigational) product or procedure (attribution of ‘unrelated’, ‘unlikely’, ‘possible’, ‘probable’, or ‘definite’). Examples of Adverse Events that will be recorded in this study are:

- Concomitant illness
- Physical injury
- Events possibly related to medication

- Significant worsening (change in nature, severity, or frequency) of the disease under study or other pre-existing conditions
- Drug interactions
- A laboratory or diagnostic test abnormality occurring shortly after the start of the study that results in the withdrawal of the patient from the study, requires medical treatment or further diagnostic work-up, or is considered by the study investigator to be clinically significant

Adverse events will be graded according to the NCI Common Toxicity Criteria, Version 4.0.

#### Serious Adverse Event (SAE)

A serious adverse event is any untoward medical occurrence resulting in one or more of the following:

- Results in death or ANY death occurring within 28 days of last dose of study drug (even if it is not felt to be drug related)
- Is life-threatening (defined as an event in which the patient was at risk of death at the time of the event; it does not refer to an event which hypothetically might have caused death if it were more severe)
- Requires inpatient hospitalization or prolongation of existing hospitalization

NOTE: Hospitalizations that are not considered SAEs are:

- Hospitalization for elective treatment of a pre-existing condition unrelated to study participation
- Results in persistent or significant disability/incapacity
- Is a congenital anomaly or birth defect
- Is an important medical event (defined as a medical event(s) that may not be immediately life-threatening or result in death or hospitalization but, based upon appropriate medical and scientific judgment, may jeopardize the patient or may require intervention (e.g., medical, surgical) to prevent one of the other serious outcomes listed in the definition above). Examples of such events include, but are not limited to, intensive treatment in an emergency room or at home for allergic bronchospasm; blood dyscrasias or convulsions not resulting in hospitalization; or the development of drug dependency or drug abuse.

#### Unexpected Adverse Event

An adverse event not mentioned in the package insert or the specificity or severity of which is not consistent with the package insert.

## Determining Attribution to the Investigational Agent(s)

**Attribution:** An assessment of the relationship between the AE and the medical intervention. CTCAE does not define an AE as necessarily “*caused by a therapeutic intervention*”. After naming and grading the event, the clinical investigator must assign an attribution to the AE using the following attribution categories:

Relationship	Attribution	Description
Unrelated to investigational agent/intervention	Unrelated	The AE is clearly NOT related
	Unlikely	The AE is doubtfully related
Related to investigational agent/intervention	Possible	The AE may be related
	Probable	The AE is likely related
	Definite	The AE is clearly related

## Adverse Event (AE) Reporting

Adverse events (AEs) will be reported to the principal investigator immediately and will be recorded from the time of randomization (approximately 30 days after surgery), regardless of whether or not the event(s) are considered related to trial procedures or medications. All AEs considered related to trial medication will be followed until resolution, return to baseline, or deemed clinically insignificant, even if this occurs post-trial.

### Reporting to the IRB:

1. Unanticipated problems involving risks to subjects or others will be reported **promptly** to the IRB if they:
  1. were unexpected;
  2. were related or possibly related to study participation; AND
  3. suggests that the research places subject(s) or others at greater risk of harm than was previously known.

If the serious adverse event does not meet all three (3) criteria listed above, the event does not have to be promptly reported to the Indiana University IRB.

2. **Prompt** reporting of unanticipated problems to the IRB is defined as within 5 business days of the study team becoming aware of the event.

## 10.0 Study Withdrawal/Discontinuation

Subjects may withdraw from the trial at any time at their own request, or they may be withdrawn at any time at the discretion of the investigator for any reason. If the patient withdraws from the trial and also withdraws consent for disclosure of future information, no further evaluations should be performed and no additional data should be collected. The investigator may retain and continue to use any data collected before such withdrawal of consent.

## **11.0 Statistical Considerations**

Univariate analysis will be done to describe the distribution of the sample in terms of demographics (age, race, sex, BMI), pre-treatment medical history, pre-treatment concomitant medication. The distribution of the sample will be reported in terms of mean ( $\pm$ SD), median (Inter-quartile range), or percentage depending upon the type of variable (continuous or categorical). Bivariate analysis comparing the sociodemographic variables of the treatment groups will be conducted using chi squared, student T tests, Mann U Whitney, and ANOVA followed by Tukey's pairwise comparison of the means as appropriate.

Intent-to-treat analysis of the data from the baseline and follow-up visits will be analyzed in order to compare the renal functions after liver transplant between the study arm (those receiving Everolimus + mycophenolic acid) and the control arm (those maintained on the low dose Tacrolimus monotherapy + mycophenolic acid therapy). Repeated measures analysis will be conducted to analyze measures of renal function after liver transplant across the treatment groups using multivariable generalized linear model (GLM) over time accounting for the correlation of the measurements obtained for each patient over time. For the secondary end-points, bivariate analysis will be done to compare the outcomes between the treatment and the control groups. Pearson's chi-square, student T tests, and Mann U Whitney tests as appropriate. Adjustment for the correlated variance due to repeated measures will be made throughout the analysis. All analysis will be conducted at 0.05 level of significance using Stata/SE version 14.2 (StataCorp., 2015).

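### Section 11 does not commit to adjusting the primary renal-function model for pre-randomisation GFR, and its wording lets baseline enter as an ordinary response row

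*Combined protocol and SAP*

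**What the plan says.** Section 11.0 is the only description of the primary analysis. It says: "Intent-to-treat analysis of the data from the baseline and follow-up visits will be analyzed in order to compare the renal functions". The method is a repeated-measures analysis "using multivariable generalized linear model (GLM) over time accounting for the correlation of the measurements obtained for each patient over time". No covariate is named. The text does not say whether baseline GFR is a covariate, a response or the base of a change score. It mentions no group-by-time term and no single treatment contrast.

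The Primary Aim in section 2.0 names GFR without a time point. On follow-up, section 7.0 says: "Data will be collected at 6 month, 12 month, 24 month, and 36 month timepoints. GFR will be measured at these time points". None of the four visits is ranked first. Table 1 marks MDRD GFR at all 16 columns, ten of them after day 30.

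Baseline GFR is not defined. The baseline information listed in section 7.0 covers demographics, history and medication, and Table 1 has both a day 0 and a day 30 column. Three statements point to day 30:

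- Eligibility (section 4.0) depends on GFR "at 30 days post-operatively +/- 7 days".
- Section 6.0 says: "On POD 30, patients meeting study criteria will be randomized to either the study arm or control arm".
- Section 7.0 says: "The treatment period starts at 30 days post transplant".

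The sample size in section 5.0 was obtained "using the two independent-groups and two-tail t-tests", on creatinine clearance, with no covariate and no stated visit.

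**The concern.** Every participant must have a GFR near day 30 to qualify, so a pre-randomisation value of the primary outcome will exist for all of them. The plan does not commit to using it. Two things follow.

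- **Precision.** If day-30 GFR predicts later GFR, leaving it out of the model gives a wider interval than the same patients could provide. The planned design has almost no margin above 80% power.
- **Dilution.** Section 11.0 puts baseline and follow-up data into one model over time. Read literally, this allows baseline to be stacked as another response row. Randomised arms cannot differ systematically before treatment, so a group main effect averaged over all rows includes one row where the true difference is zero. The tested quantity is then smaller than the follow-up effect.

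With the contrast unnamed, the choice among these analyses could also be made after the data are seen, in an open-label trial.

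**Working it through.** **Inputs.** From section 5.0: means 65 and 57 mL/min (difference 8), SDs 14 and 13, 46 evaluable per arm, two-sided 0.05, attrition 11%. Assumed, because the documents do not give them: the correlation b between day-30 and follow-up GFR, the common within-patient correlation ρ, and the ratio k of baseline SD to follow-up SD. Power is from the noncentral t distribution.

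**Step 1: the plan's own figure.** Pooled SD s = √((14² + 13²)/2) = √182.5 = 13.51. SE = 13.51 × √(2/46) = 2.817, and 8/2.817 = 2.84. With 90 df the power is 80.2% and the 95% CI half-width is 1.987 × 2.817 = 5.60. Allowing for attrition, 46/0.89 = 51.7, so 52 per arm and 104 in total. The stated figures reproduce.

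**Step 2: day-30 GFR as a covariate, one visit.** Residual variance is s²(1 − b²) with 89 df. Chance imbalance in the covariate multiplies the variance by about 1 + 1/(2n − 4) = 1 + 1/88 = 1.011.

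| b | Power without imbalance term | Power with imbalance term | Half-width with imbalance term |
|---|---|---|---|
| 0 | 80.2% | 79.8% | 5.63 |
| 0.1 | 80.6% | 80.2% | 5.60 |
| 0.3 | 83.8% | 83.4% | 5.37 |
| 0.5 | 90.0% | 89.7% | 4.87 |
| 0.7 | 97.6% | 97.4% | 4.02 |

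The lost degree of freedom moves the critical value only from 1.9867 to 1.9870. The imbalance term is the larger cost, and it is still small. Break-even is near b = 0.1.

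**Step 3: baseline as a response row, group main effect tested.** With m follow-up rows and one baseline row, the tested effect is 8m/(m + 1): 8 × 4/5 = 6.4 for four rows, and 8 × 10/11 = 7.27 for ten. The variance of a patient's mean is s²[k² + m + m(m − 1)ρ + 2mkρ]/(m + 1)². For m = 4 and k = 1 this is 182.5(1 + 4ρ)/5, or 138.7 at ρ = 0.7. Then SE = √(2 × 138.7/46) = 2.456 and 6.4/2.456 = 2.61. For comparison, the mean of the four follow-up visits alone has effect 8 and variance s²(1 + 3ρ)/4.

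| Power at ρ = | 0.3 | 0.5 | 0.7 |
|---|---|---|---|
| Four follow-up rows plus baseline, equal SDs | 92.3% | 82.7% | 73.2% |
| Four plus baseline, baseline SD 0.7 of follow-up | 94.9% | 86.9% | 78.3% |
| Ten plus baseline, equal SDs | 98.9% | 93.3% | 85.0% |
| Four follow-up rows, baseline left out, unadjusted | 98.3% | 94.5% | 89.1% |

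Two of the nine diluted scenarios fall below 80%. With four rows and equal SDs, stacking baseline costs 98.3 − 92.3 = 6.0, 94.5 − 82.7 = 11.8 and 89.1 − 73.2 = 15.9 percentage points against leaving it out.

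**Step 4: does the choice of contrast matter?** The last row assumes 8 mL/min at every visit. If the difference instead grew as 2, 4, 6, 8 (an assumption), the four-visit average would be 20/4 = 5. Unadjusted power would then be 60% at correlation 0.5 and 51% at 0.7, against 80.2% for month 36 alone. The average is therefore a trade-off.

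**The case against.** The strongest reply is that section 11.0 already leaves room for the right analysis. A multivariable model permits a baseline covariate, a model over time permits a group-by-time test, and a model with baseline as a response is sound if the arms share one baseline mean. Nothing says that a main effect including the baseline row will be tested. This stands: the gap is a missing commitment, and dilution is something the wording allows, not something the plan states.

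A second reply is that the benefit rests on a correlation that the documents do not give, and that restricting entry to GFR of 60 or below may reduce it. This also stands. The figures near 90% and above need b of about 0.5 or more.

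A third is that adjustment is not free. This is right, but the cost is small: at b = 0 power falls by about 0.4 points (80.2% to 79.8%), and at b = 0.1 there is no gain.

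A reader might infer that an unadjusted analysis would be biased or invalid. Randomisation protects the unadjusted post-randomisation comparison. A reader might also infer from the 73.2% that the trial is underpowered. That figure belongs to one unfavourable combination of assumptions under an analysis the plan does not specify.

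**Conclusion.** The point holds as a gap in commitment and efficiency. Section 11.0 fixes neither the role of baseline GFR nor the tested contrast, although a suitable covariate is already required for entry and scheduled in Table 1.

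Adjustment changes single-visit power by between about −0.4 points (b = 0) and +17.2 points (b = 0.7: 97.4 − 80.2). Where the trial falls in that range cannot be settled from the documents. The dilution shrinks the tested effect by one fifth with four follow-up rows and by one eleventh with ten. Whether power then drops below 80% depends on the correlation, the SD ratio and the number of rows.

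All figures take the SDs from section 5.0, which are for creatinine clearance, and assume 46 evaluable per arm and a constant 8 mL/min.

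The unnamed contrast, taken alone, is missing detail. It does not follow that the four-visit average is the only defensible contrast. The section 5.0 total reproduces and is not challenged, but one unadjusted t-test on creatinine clearance does not directly give the power of a four-visit MDRD average.

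**What to change.** Amend section 11.0 before any outcome comparison by arm:

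1. Define baseline as the last MDRD GFR on or before randomisation. MDRD GFR is the only row labelled GFR in Table 1. The on-or-before rule is needed because the eligibility window runs 7 days either side of day 30.
2. Use only post-randomisation GFR as responses, with baseline GFR as a covariate. Alternatively, keep baseline in a model that constrains the arms to a common baseline mean.
3. State that no group main effect that includes the baseline row will be tested.
4. Name one primary treatment contrast. The adjusted difference averaged over 6, 12, 24 and 36 months is one example; a single visit is another. The sponsor should choose according to when the effect is expected, and state the power for that choice.

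The cost is a few sentences. No extra visits, patients or assays are needed. The statistical price is one degree of freedom for a single linear term, plus about 1% in variance if day-30 GFR turns out not to predict later GFR.
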